3.4. Primary Safety Endpoint

Patients will be asked to report on the tolerability of the gummies. Safety labs will be drawn at baseline and at subsequent study visits to monitor for any adverse effects. These labs include CBC, BMP, and LFT's which will allow the Investigator to screen for any baseline blood values that could be considered clinically significant prior to study entry, and then continue to monitor throughout the trial. Additional blood from the draw will be sent to the Institute of Ethnomedicine to be tested for the amount of L-serine present.

4 Subject Selection and Withdrawal

4.1 Inclusion Criteria

1. Diagnosis of early stage Alzheimer's disease as scored by the Clinical Dementia Rating Scale score of 0.5 -1.0 upon enrollment.
2. Participants able to provide informed consent.
3. Participants taking NMDA receptor antagonist medications or acetylcholinesterase inhibitor medications must be on a stable dose of these medications for at least 30 days prior to enrolling in this clinical trial.
4. Participants able to consume study gummy chews throughout the course of the clinical trial.

4.2 Exclusion Criteria

1. Diagnosis or previous history of ischemic stroke, astrocytoma, meningioma or oligodendroma.

2. Diagnosis or previous history of any other comorbid diagnosis of neurodegenerative disease including amyotrophic lateral sclerosis, Parkinson's disease, Lewy Body Disease, Pick's Disease, Huntington's Disease, or Progressive Supra Nuclear Palsy.
3. Undergoing any chemotherapy or radiation therapy for any tumor or carcinoma.
4. Diagnosis or previous history of type I or type II diabetes. Subjects with no history of diabetes will have a hemoglobin A1C test as part of their initial labs at V1. Subjects with a Hgb A1C value of less than 6.5 will be considered eligible. Subjects will be referred to their PCP if their Hgb A1C indicates they may be at increased risk to develop diabetes, though will be allowed to participate if they meet all other inclusion/exclusion criteria, and if deemed appropriate by the Investigator.
5. Diagnosis or previous history of psychiatric illness that in the investigator's opinion would affect the subject's ability to successfully participate in the study.
6. In the Investigator's opinion, subject would be unable to successfully participate in the study for any reason.

4.3 Subject Recruitment and Screening

Participation in this research requires informed consent according to Institutional Review Board (IRB) guidelines. A signed IRB approved Consent Form is the means of documenting this understanding. Subjects must be able to consent for themselves to be able to participate in this study and have received an exact copy (at point of signature acquisition). Potential recruits are instructed that their participation is completely voluntary and that their medical care will not be altered in any way should they elect not to participate. Subjects are recruited from patients presenting to the Dartmouth-Hitchcock Medical Center Department of Neurology in [name] practice or referred by outside neurologists to the department. All study enrollment, visits and procedures will take place at Dartmouth Hitchcock Medical Center, Lebanon, NH.

4.4 Early Withdrawal: When and How to Withdraw Subjects

Participants taking NMDA receptor antagonist or Acetylcholinesterase inhibitor medications must be on a stable dose for 30 days prior to beginning the study. Participants may come off these medications during the course of the study if it is in their best interest, though should consult with the PI regarding this decision. Participants will be asked to refrain from starting NMDA receptor antagonist or Acetylcholinesterase inhibitor medications throughout the duration of this trial. If they wish to begin these therapies, they may opt to do so and be withdrawn from this clinical trial

Participants will be placed on an ascending dose for two weeks of 2 x 1g gummies BID, two weeks of 8 x 1g gummies BID, and then provided the target dose of 15 x 1g gummies BID for 36 weeks if they are able to tolerate these doses without negative effects. If a patient cannot tolerate 2 or 8g (BID) they will cease treatment. If a patient can tolerate 8g (BID) but not 15g (BID), they will remain in the study through the remainder of the study timeline taking a total of 15g per day (1 package of gummies split into two time periods within the day). The same escalating dose schedule and procedures will be observed for both placebo and L-serine patients. If a participant experiences an adverse event which is serious in nature, and deemed to be drug related, the study medication will be discontinued immediately. The Investigator may reserve the right to discontinue a subject from treatment if the PI feels it is not in the best interest of the participant to continue in the study.

If a participant discontinues study medication they will be encouraged to remain in the study and complete study related procedures and assessments while not receiving study medication.

If a participant discontinues study medication and does not wish to return for the remainder of study visits, this decision will be documented. They will be asked to return to the site for a final study visit. This visit will be conducted with the same study procedures and assessments as "Visit 4" listed in Section 6.5.

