3.1 General Design

This is a Phase IIa, randomized, double-blind, placebo controlled trial. Potential subjects for participation in this study will be identified by the Investigator based on their clinical and radiographic diagnosis of Alzheimer's disease, which will be completed as part of standard care. Up to 40 subjects will be enrolled. Subjects participating in the study will be randomized to receive either gummies containing L-Serine or placebo gummies, with the Investigator and study staff blinded to the group assignments. An individual subject's participation in the study will last approximately 40 weeks from time of enrollment. Study office visits will take place at Day 0, week 12, week 24 and week 36. Phone contact will be made at week 2, week 4 and week 8 to assess compliance, adverse events and concomitant medication. A follow-up phone call will also be made at week 40 to inquire about adverse events, concomitant medication, subject impression of study, subjective L-serine tolerability, and if they are continuing L-serine supplementation. If, due to study-related events, the PI judges that a participant should be seen in office during study participation, a visit will be scheduled (Unscheduled Visit)

The Day 0 visit includes subject consent, administration and scoring of the Clinical Dementia Rating Scale, review of medical history including any family history of Alzheimer's disease, a brief neurological and physical exam, capture and grading of baseline conditions, and a review of concomitant medications. Hemoglobin A1C, safety labs (CBC, BMP) and research only blood draw will be completed. Eligibility will be confirmed by the PI prior to randomization. If a participant fails to qualify based on their CDR score or Hgb A1 level, the portion of their blood drawn for research only will be discarded.

All subsequent study visits include a brief physical/neurological exam, adverse event assessment, study medication compliance assessment, concomitant medications review, safety blood draws (CBC, BMP) and research-specific blood draws.

Study medication will be dispensed at Day 0, week 12, and week 24, and collected at week 12, week 24 and week 36. All unused study drug will be collected and returned to the study sponsor.

The MoCA will be performed at Visits 0, week 24, week 36, and at early withdrawal or unscheduled visits. Three different MoCA versions will be administered in a random order during these assessments.

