3.2 Primary Endpoint

This proof-of-concept trial will assess the MoCA score at the week 36 study visit in patients with L-serine treatment compared to placebo. Slopes reflecting the change in MoCA score from Day 0 to the week 36 visit will be compared between treatment and placebo groups.

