4.4.2 Data Collection and Follow-up for Withdrawn Subjects

If a patient is terminated early from the study as a result of an adverse event, every effort will be made to follow the patient until the adverse event resolves.

5 Study Drug

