7.2 Statistical Methods

Nonparametric statistics are proposed since it is not known in advance if MoCA scores or levels of neurally-derived exosomes will approximate, or can be transformed, to a normal distribution. A Mann-Whitney U-test will compare exosomal protein levels or MoCA scores between the L-serine treatment and placebo patients at a $p < 0.05$ level. Parametric equivalents will be considered if appropriate to the distribution of the data.

First, we will check the effectiveness of the randomization by comparing the baseline characteristics of the L-serine and placebo groups according to demographic factors (e.g. age, gender). We will also assess whether the levels of biomarkers or cognitive impairment in the treatment group differ from the placebo group at time zero. This first test will check whether the randomization procedures were sufficient for the study. Next we will compare the exosomal protein levels or MoCA scores at the last study visit (month 9). (H_0 = there is no difference between the median exosomal protein level or MoCA score for treatment patients and control patients; H_1 = there is a difference between the median exosomal protein level MoCA score for treatment patients and control patients). A Mann-Whitney U-test will examine exosomal protein levels or MoCA scores of each patient, by comparing median values between groups. Second, we will assess the slope of the exosomal protein levels or MoCA scores over time to see if they differ among the treatment and control groups by Mann-Whitney U-test. We will use Spearman's Rank correlation, in which rho is the equivalent of the parametric correlation coefficient, to determine if there is a monotonic relationship between levels of proteins in the neurally-derived exosomes and the MoCA scores.

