7.3 Subject Population(s) for Analysis

The subject populations whose data will be subjected to the study analysis – both for the primary analysis and any applicable secondary analyses include:

Any subject randomized into the study that received at least one dose of study drug.

8 Safety and Adverse Events

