***Please Note:**

Plasma = **Yellow** tops

Buffycoat = **Clear** tops

Erythrocyte = **Red** tops

Shipping instructions

1. Prior to placing the specimens in the shipping containers, verify that all tubes have been properly identified.
2. Verify that the specimens match those listed on the Laboratory Requisition Form.
3. Be sure to inspect the shipping boxes for accurate labeling information.
4. Remove the box containing the vials from the freezer.

5. Place a layer of dry ice at the bottom of the frozen shipper.
6. Ensure that the absorbent sheet is placed in the transport bag with the box of cryovials. Place the lab requisition into the outer pouch of the bag. It is acceptable to ship the entire box of specimens from more than one patient together in the transport bag.
7. Seal the transport bag and place it into the bottom of the shipping box.
8. Fill the remainder of the box with dry ice (minimum of 8 lbs or ~4 kg). Place the Styrofoam cover on the inner Styrofoam container. **DO NOT TAPE THE STYROFOAM BOX CLOSED.**
9. Close box flaps and seal the exterior box with tape.
10. Complete the necessary sections on the pre-printed FedEx Air Waybill. Date all forms where necessary and retain the "Sender's Copy" for files. Place completed air waybill into the clear plastic air bill pouch face up. Make sure outside of box has been properly marked with amount of dry ice.

- **Packages will be shipped frozen on dry ice to Brain Chemistry Lab approximately every 4-6 weeks.**
- **Brain Chemistry Lab will be notified by email with fed ex tracking number when labs have been shipped.**
- **Other arrangements can be made prior to shipping with prior approval by both parties.**

L-Serine Study Timeline of Events-
LSPI-2
D16180

		+/- 2 week	+/- 2 week	+/- 2 week	+/- 2 week	+/- 2 week	+/- 2 week	+/- 2 week	
	Day 0 Visit 1	Week 2 Phone Call	Week 4 Phone Call	Week 8 Phone Call	Week 12 Visit 2	Week 24 Visit 3	Week 36 Visit 4	Week 40 Follow-Up Call	Early Withdrawal/ Unscheduled Visit
Procedures									
Consent	x								
Clinical Dementia Rating Scale	x								
Medical History	x								
Adverse event tracking		x	x	x	x	x	x	x	x
Drug Collect/accountability					x	x	x		x
Medication compliance inquiry		x	x	x	x	x	x		x
Concomitant Medication	x	x	x	x	x	x	x	x	x
Neuro/Physical Exam	x				x	x	x		x
MoCA (Montreal Cog Assessment)	x					x	x		x

Gummy dispense and instruction	x				x	x			
Medication calendar issue and instruction	x				x	x			
Continued Supplementation Status								x	

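### Section 7.1 calls the sample adequate after dropout with no dropout rate and no reserve, and 7.2/7.3 do not say how a participant without a week-36 MoCA is analysed

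*Combined protocol and SAP*

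**What the plan says.** **Sample size (7.1).** With a MoCA SD of about 4 and 20 patients per arm, the minimum detectable difference is given as 3.65 points. The exosome marker (SD 2.8) is given 2.5 pg/ml at power 0.8. Mead's resource equation then yields E = 37 against a usual value of about 20. The section closes by accepting that patients may drop out before week 36 and stating that the sample will still provide the power needed. It gives no dropout rate.

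**Endpoint and analysis (3.2, 7.2, 7.3).** The primary endpoint is the MoCA at week 36, and also: "Slopes reflecting the change in MoCA score from Day 0 to the week 36 visit will be compared between treatment and placebo groups". Section 7.2 applies Mann-Whitney tests to the month-9 scores and to the slopes. The analysis population in 7.3 is: "Any subject randomized into the study that received at least one dose of study drug".

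**When MoCA is collected (3.1, visit grid).** "The MoCA will be performed at Visits 0, week 24, week 36, and at early withdrawal or unscheduled visits".

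**Withdrawal (4.4, 4.4.2).** On starting a cholinesterase inhibitor or NMDA antagonist: "If they wish to begin these therapies, they may opt to do so and be withdrawn from this clinical trial". Later in the same section: "If a participant discontinues study medication they will be encouraged to remain in the study and complete study related procedures and assessments". Section 4.4.2 covers only termination for an adverse event, where "every effort will be made to follow the patient until the adverse event resolves".

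**The concern.** The statement in 7.1 is a claim about a property of the design. If 3.65 points can be detected only with every patient evaluable, the plan has no reserve at that difference, and the reader is given a figure that the completed trial is unlikely to match.

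Sections 7.2 and 7.3 also leave a gap between who is in the analysis population and who has a score to compare. Someone dosed once and lost after week 24 belongs to the population but has no month-9 value. With 40 patients, a few such cases can change a result near the threshold, and a rule chosen once the data are known would weaken any efficacy signal.

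**Working it through.** **Inputs.** SD 4, 20 per arm and 3.65 points are from 7.1. Alpha 0.05 is from 7.2, and the non-directional alternative there makes the test two-sided. Power 0.80 is stated in 7.1 for the exosome marker only; I assume it for MoCA. No dropout rate is given, so losses of 10%, 20% and 30% are assumptions.

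**Step 1: reproduce 3.65.** SE = SD × √(1/n₁ + 1/n₂) = 4 × √(1/20 + 1/20) = 1.265. Non-centrality = 3.65/1.265 = 2.886 on 38 degrees of freedom, with critical t = 2.024. Noncentral-t power is 80.3%, and solving for exactly 80% gives 3.64 points. The stated figure is therefore a two-sided t-test result with the full 20 per arm. The normal approximation gives 3.54 and a one-sided t-test 3.20; neither matches.

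**Step 2: remove patients.** The formula is the same. Mann-Whitney values come from simulated normal data with SD 4. At 20 per arm, one run of 8,000 trials gave 78.7% and one of 40,000 gave 78.0%.

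| Evaluable | Assumed loss | SE | t-test power at 3.65 | t-test detectable (80%) | Mann-Whitney power at 3.65 | Mann-Whitney detectable |
|---|---|---|---|---|---|---|
| 20 v 20 | none | 1.265 | 80.3% | 3.64 | 78–79% | about 3.7 |
| 20 v 19 | one patient | 1.281 | 79.2% | 3.69 | – | – |
| 18 v 18 | 10% | 1.333 | 75.8% | 3.85 | about 73% | about 4.0 |
| 16 v 16 | 20% | 1.414 | 70.5% | 4.09 | about 67% | about 4.3 |
| 14 v 14 | 30% | 1.512 | 64.2% | 4.40 | about 60% | about 4.6 |

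**Step 3: test Mead's equation as support.** E = 39 − 1 − 1 = 37. E would still equal 20 with N − 1 = 22, that is 23 patients (12 v 11). MoCA t-test power at 3.65 is then about 55%. The equation counts error degrees of freedom and contains no effect size, SD or power.

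**Step 4: the slope comparison.** If the SD is 4 at both visits and the scores correlate ρ, the SD of change is 4 × √(2(1 − ρ)). The documents do not give ρ. For a 3.65-point difference in change:

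| Assumed ρ | SD of change | Power, 20 per arm | Power, 16 per arm |
|---|---|---|---|
| 0.5 | 4.00 | 80.3% | 70.5% |
| 0.6 | 3.58 | 88.2% | 79.7% |
| 0.7 | 3.10 | 95.3% | 89.7% |

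Above ρ = 0.5 the slope comparison has more reserve than the week-36 score; below it, less.

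**Step 5: look for a missing-score rule.** Take a dosed participant with MoCA scores at Day 0, week 24 and early withdrawal but none at week 36. Section 7.3 includes this person. Under 7.2, three treatments are all compatible with the text: leave them out of both tests; use the last score in place of month 9; or compute a slope from the scores available. Section 9.3 requires missing CRF entries to be explained, which is a recording rule and not an analysis rule.

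**Step 6: the 4.4 wording.** The request to complete assessments, and the final visit for those who will not return, are both triggered by discontinuing study medication. The sentence on starting new therapy speaks of withdrawal from the trial. Section 4.4 does not say whether the first covers the second. Section 5.6 says that no concomitant medication is prohibited, while 4.4 withdraws participants for starting these two classes.

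**The case against.** - **3.65 is a detectable difference, not a target effect.** This stands. The plan names no target and does not define the power needed. A 10% loss moves detectability only from 3.64 to 3.85 points, a small change for a proof-of-concept trial aimed at tolerability and preliminary efficacy. The inference that the trial is too small or must enrol more therefore does not follow. What fails is the statement that dropout leaves power adequate.
- **The slope is also in the primary endpoint and may be better powered.** This stands as a possibility, but it depends on a correlation that 7.1 does not use or state.
- **The exosome marker has slack, since 7.1 cites a difference of about 7 pg/ml.** That is a between-stage difference, not a treatment effect. At the stated 2.5 pg/ml, t-test power is 78.6% at 20 per arm and 74.0% at 18 (normal approximation: 80.6% and 76.4%).
- **Section 4.4 already covers those who start a new drug.** This largely stands. Study drug comes only through the trial, so withdrawal would ordinarily mean stopping it, and the later clauses then apply on a natural reading. A MoCA is also scheduled at early withdrawal. A reader might infer that these participants leave with no late outcome data; the documents do not support that. Only their week-36 score is uncertain.
- **Losses through new therapy would bias the comparison.** A reader might infer this because people who are declining seem likelier to start treatment. The documents give no frequency and no link to decline, and the rule is the same in both arms, so no bias is expected from it if L-serine has no effect. Any figure for bias would rest on invented values.

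**Conclusion.** The arithmetic behind 3.65 is right. The claim that the sample stays adequate after dropout is not supported. At that difference one lost patient takes t-test power below 80%, a 10 to 20% loss takes it to 75.8–70.5%, and the planned Mann-Whitney test starts at about 78–79% and falls to about 73–67%. These figures assume normal data, SD 4, equal loss in each arm, and 80% as the intended MoCA power. Mead's equation does not change this.

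Separately, 7.2 and 7.3 lack a rule for dosed participants without a week-36 MoCA and make no stated use of the week-24 and early-withdrawal scores in its place. This gap applies to every cause of dropout. The 4.4 wording is a secondary clarification. The points should be corrected before analysis; they do not undermine the design.

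**What to change.** 1. **Section 7.1.** Replace the adequacy statement with the power or detectable difference under a stated dropout assumption, for example 3.85 points at 10% loss and about 4.1 at 20% (t-test), or about 4.0 and 4.3 for Mann-Whitney. Do not rest it on Mead's equation. No added enrolment.
2. **Sections 7.2 and 7.3.** Keep the Mann-Whitney tests and state who enters each. Add a supportive baseline-adjusted repeated-measures analysis using the week-24 and early-withdrawal MoCA scores already collected. Fix it before unblinding and before any comparison by arm. Section 7.2 already allows parametric methods where the distribution permits.
3. **Section 4.4, as a clarification.** State that the existing request to complete assessments also covers participants withdrawn for starting a cholinesterase inhibitor or NMDA antagonist. The medication rules stay as they are. Sections 4.4 and 5.6 must be reconciled.

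**Cost.** A few sentences, a slightly less favourable stated figure and a little more analysis; no new visits. Scores obtained after new therapy may include that drug's effect, so report the supportive analysis with and without them. Without them, it relies on the earlier scores explaining who leaves. A participant seen at early withdrawal and again at weeks 24 and 36 would have four MoCAs against the three versions in 3.1, so version reuse should be recorded.

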4.4.1 Dosing delays and dose modifications

Dose modification for the following adverse events: nausea, vomiting, diarrhea will proceed as follows:

Nausea, vomiting, diarrhea	Management/Next Dose for L-serine
≤ Grade 1	No change in dose
Grade 2	Hold until ≤ Grade 1. Resume at same dose level.
Grade 3	Hold* until < Grade 2. Resume at one dose level lower, if indicated.**
Grade 4	Off protocol therapy
*Patients requiring a delay of >2 weeks should go off protocol therapy.	
**Patients requiring > two dose reductions should go off protocol therapy.	
Recommended management: antiemetics, or antidiarrheal therapy.	

Adverse events will be classified using the Common Terminology Criteria for Adverse Events (CTCAE) Version 4.03, June 14, 2010.

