1.5 Dose Rationale and Risk/Benefits

Since there is no literature as to how much L-serine is tolerated or beneficial in eAD patients, we considered doses generally tolerated by humans in the above reported clinical trials. The dose selected for this trial will be 30g/day as this dose was well-tolerated by both ALS patients and HSAN1 patients. L-serine will be administered orally through gummies being produced in a GMP compliant facility (Knechtel, Chicago, IL). Each gummy contains 1 g L-serine (treatment) and will be packaged in a foil packet containing 15 pieces to be taken both morning and evening (with or without food) for nine months. The placebo will be a gummy with no L-serine, packaged and taken in the same manner.

Although chewing this quantity of gummies, and the dose of 30g/day of L-serine has been well tolerated by other neurological patients, we will monitor side-effects in these eAD patients during a dose ramp-up period. We will also monitor amino acid balances in blood serum samples. In order to assess tolerability in patients, we have designed a 4 week dose ramp-up. Patients will take 2g (BID) for the first two weeks followed by 8g (BID) for the next two weeks. If patients tolerate these doses without negative effects, then they will begin taking 15g (BID) for the remainder of the study. If a patient cannot tolerate either 2 or 8g (BID) they will be dropped from the study, however, if a patient can tolerate 8g (BID) but not 15g (BID), they will remain in the study through an additional 246 day period taking a total of 15g per day (1 package of gummies split into two time periods within the day). The same ramp-up schedule and procedures will be observed for both placebo and L-serine patients.

2 Study Objective

Determine tolerability of L-serine for early stage Alzheimer's disease patients and assess preliminary indications of efficacy. Efficacy will be assessed by cognitive testing and biomarkers in plasma.

3 Study Design

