5.1 Description

L-serine is a naturally-occurring, non-essential amino acid present in the human diet. L-serine will be presented in gummies containing 1g serine each. Gummies will be packaged into a foil package containing 2, 8, or 15 gummies with instructions to take one package in the morning and one in the evening, for a total of 4, 16, and 30g of L-serine/day, respectively. Placebo gummies containing no L-serine will be packaged in the same manner and given to patients to take two times a day.

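### Sections 1.5 and 4.4 disagree on whether a patient who cannot tolerate 2 or 8 g BID stays in the study, and neither is reconciled with the dose-reduction table in 4.4.1

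*Combined protocol and SAP*

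**What the plan says.** **Section 1.5** describes the four-week ramp-up (2 g BID, then 8 g BID). On escalation it says "If patients tolerate these doses without negative effects, then they will begin taking 15g (BID) for the remainder of the study". On failure it says "If a patient cannot tolerate either 2 or 8g (BID) they will be dropped from the study". A patient who manages 8 g BID but not 15 g BID stays in the study on a fallback of 15 g/day.

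**Section 4.4** deals with the same failure differently: "If a patient cannot tolerate 2 or 8g (BID) they will cease treatment". Later in the section, anyone who stops study medication is encouraged to stay on and complete the study assessments off drug. The fallback from 15 g BID matches 1.5: "taking a total of 15g per day (1 package of gummies split into two time periods within the day".

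**Section 4.4.1** is a graded table for nausea, vomiting and diarrhea. Grade 2 is held and resumed at the same level. Grade 3 is held, and then "Resume at one dose level lower, if indicated". Therapy ends at Grade 4, after a delay of more than two weeks, or under the footnote "Patients requiring > two dose reductions should go off protocol therapy". The table is not restricted to any dose step or period.

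**Section 5.1** gives the only list of levels: "Gummies will be packaged into a foil package containing 2, 8, or 15 gummies", one pack morning and evening, "for a total of 4, 16, and 30g of L-serine/day, respectively".

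**The concern.** Sections 1.5 and 4.4 start from the same trigger and end in different places. A site following 1.5 takes the patient out of the study. A site following 4.4 stops the drug and tries to keep the patient in follow-up. Section 3.2 makes the week-36 MoCA the primary endpoint, so the choice decides whether that value is sought for these patients. Section 7.3 keeps every randomized and dosed patient in the analysis population, and section 7 gives no method for missing values. A patient dropped under 1.5 would therefore belong to the analysis without a week-36 score.

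The table in 4.4.1 adds to this. It allows dose reduction at steps where 1.5 and 4.4 only stop treatment, and it uses a term (dose level) that no section defines. Tolerability is the first-named objective in section 2, so the rules for patients with gastrointestinal trouble should be unambiguous.

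**Working it through.** **Dose levels.** From 5.1, gummies per pack × 1 g × 2 intakes: 2 × 2 = 4, 8 × 2 = 16, 15 × 2 = 30 g/day. The stated totals reproduce. The fallback in 1.5 and 4.4 is one 15-gummy pack split over the day: 15 g/day, or 15 / 2 = 7.5 g per intake. It is not one of the three listed totals.

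**The rules side by side.** The first two columns apply if the patient is judged unable to tolerate the dose. The third assumes that dose level means the 4/16/30 g/day scale.

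| Grade 3 event at | 1.5 | 4.4 | 4.4.1, one level lower |
|---|---|---|---|
| 2 g BID | out of study | off drug, follow-up encouraged | no lower level exists |
| 8 g BID | out of study | off drug, follow-up encouraged | 4 g/day |
| 15 g BID | 15 g/day | 15 g/day | 16 g/day |

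- The first two rows show the clash between 1.5 and 4.4. It does not depend on how the table is read.
- On the listed scale, 2 reductions are possible from 30 g/day, 1 from 16 and 0 from 4. The footnote's limit of more than two can never be reached on that scale. Sections 1.5 and 4.4 provide one reduction from 15 g BID and none from the lower steps.
- Grade 2 under the table means hold and resume at the same dose. Escalation in 1.5 and 4.4 requires freedom from negative effects, with no grade attached.
- Section 5.2 describes grouping of the ramp-up packs only for weeks 1–4, so supply for a later step-down is unclear.

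**Effect on power, illustration only.** Inputs from 7.1: SD 4 points, 20 per arm, detectable difference 3.65 points. The 80% power and α = 0.05 are stated there for the biomarker and assumed to apply to the MoCA. The loss of two patients per arm is my assumption; the documents give no figure. Two-sided t-test, standard error = SD × √(2/n):

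- n = 20: 4 × √(2/20) = 1.265; 3.65 / 1.265 = 2.886 on 38 df; power 0.803. The detectable difference at 80% power is 3.64, which reproduces the protocol's 3.65 closely.
- n = 18: 4 × √(2/18) = 1.333; 3.65 / 1.333 = 2.738 on 34 df; power 0.758. The detectable difference is 3.85.

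The planned test is Mann-Whitney, so these figures are approximate.

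**What a dropped patient can still contribute.** Section 3.1 and the timeline of events list a MoCA at early withdrawal. On the planned schedule the 2 and 8 g BID steps end at week 4, so a final score taken promptly would come about 36 − 4 = 32 weeks or more before the endpoint visit.

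**The case against.** The best defence is that 4.4.1 sits inside 4.4, covers only three symptoms and leaves the reduction to judgement. It can be read as graded management that comes before anyone is judged unable to tolerate a dose. Neither 1.5 nor 4.4 mentions Grade 3. A reader might infer that every Grade 3 event at 8 g BID has three contradictory mandatory outcomes. The documents do not support that, because they nowhere equate Grade 3 with intolerance. What stands is narrower: they do not state the graded-management reading either, so an event that is both Grade 3 and judged not tolerated can be handled in different ways.

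Other parts of the defence also stand:

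- The 15 versus 16 g/day difference depends on reading dose level as pack size. If 15 g/day is meant as the next level down, that step has no conflict.
- The two-reduction footnote is a stopping limit and does not entitle a patient to two reductions.
- The table governs treatment only. The conflict over follow-up lies between 1.5 and 4.4, and one can argue that 1.5 is rationale and 4.4 is operative. The protocol does not say so, and 1.5 is worded as an instruction.
- A reader might infer that these rules shift a tolerability rate. No such rate or classification is defined: 3.4 relies on patient report and safety labs.
- A reader might infer bias between arms. The trial is single-center and blinded, with the same schedule in both arms, so unequal handling is not shown. It could arise if gastrointestinal effects were more frequent on active treatment, but the documents give no figures for that.

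**Conclusion.** Wrong as written. Sections 1.5 and 4.4 give incompatible instructions for the same patient, and neither is reconciled with 4.4.1. Confidence is moderate. The clash over staying in the study is plain from the text. The clash with the table depends on two undefined terms and on the absence of a stated order of precedence.

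The consequence is avoidable loss of week-36 data among patients who fail the early steps. Its size depends on how many such patients there are, which the documents do not indicate. Under the assumed loss of two per arm the power cost is modest, about 4 to 5 percentage points (0.803 − 0.758 = 0.045). It would be a mistake to conclude that a dropped patient yields no cognitive data at all: an early-withdrawal MoCA may exist, though not at week 36. No view is taken on which dose or stopping rule is right.

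**What to change.** The sponsor and investigator should reconcile sections 1.5, 4.4, 4.4.1 and 5.1 into one rule set that:

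1. lists the dose levels once, including whether the 15 g/day fallback is one of them;
2. defines what counts as being unable to tolerate a dose and what freedom from negative effects means;
3. states how the graded table relates to the tolerability rule at each step, and which takes precedence;
4. states for each branch whether the week-24 and week-36 assessments continue.

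The clinical content of the rules is theirs to decide. The cost is a protocol amendment to wording, with no added patients, visits or procedures.
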